### 8.3.3 Treatment Phase

Study visits 1 through 12 will be conducted (Figure 6a) in the study clinic and at each of these visits the study subject will have a safety and efficacy assessment and if deemed appropriate by the investigator will receive their next sub-cutaneous administration of study immunotherapy. A 60 minute post treatment in-clinic safety assessment will be conducted.

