## **1.2 Abstract and Study Design:**

This is a randomized, parallel-group, double-blind, phase 2, single center, proof-of-concept study which will evaluate the effect of a proprietary mixed preparation of FDA approved allergens (PMA) used as a sub-cutaneously administered immunotherapy for the management of allergic rhinitis (perennial and seasonal). Participating study subjects will be required to manifest the signs and symptoms of allergic rhinitis and test positive to at least six allergens using a multi aeroallergen screen at the time of study recruitment. All subjects will undergo standard allergen skin prick testing using six Multi-Test® PC skin prick test devices (Lincoln Diagnostics, Decator, IL) or comparable skin testing technique for a total of 48 SPT. Approximately 36 total subjects will be enrolled.

Following a successful screening study visit and two week medication washout period, a 8 week treatment period will be initiated with bi-weekly study visits being undertaken, through to the end of immunotherapy, for assessment of therapeutic response and safety evaluations. Efficacy evaluation will be monitored using validated instruments that assess study subject clinical response, physician global assessment, and medication use. A safety assessment will be undertaken one month following completion of treatment.

At the screening visit (Screening Visit) a potential study subject will be required to fulfill the requirements of the study inclusion and exclusion criteria, will have a clinical evaluation including medical history and physical examination, blood draw and performance of skin testing. The study subject will then abstain from using intranasal steroids and antihistamines for two weeks and then return to the clinic for administration of sub-cutaneous PMA and post-treatment in-clinic safety evaluation. The latter evaluation period will comprise approximately 60 minutes to assess the study subject's response to PMA immunotherapy. Follow up clinic study visits will continue bi-weekly through 8 weeks and at each of these visits the study subject will receive increasing doses of PMA immunotherapy and will be evaluated for safety. Twice weekly clinical evaluation will also be performed. Following the final administration of PMA immunotherapy, a one month follow-up safety and clinical efficacy evaluation will be conducted by telephone or in the clinic. The duration of the study will be approximately 14 weeks.

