### **6.4 Criteria for Discontinuation or Withdrawal of a Subject**

The primary reason for discontinuation or withdrawal of the subject from the study or study medication should be recorded in the CRF using the following categories. For screen failure subjects, refer to Section 8.1.11.

1. Pretreatment event (PTE) or adverse event (AE). The subject has experienced a PTE or AE that requires early termination because continued participation imposes an unacceptable risk to the subject's health or the subject is unwilling to continue because of the PTE or AE.
2. Significant protocol deviation. The discovery postrandomization or after the first dose of study immunotherapy that the subject failed to meet protocol entry criteria or did not adhere to protocol requirements, and continued participation poses an unacceptable risk to the subject's health.
3. Lost to follow-up. The subject did not return to the clinic and attempts to contact the subject were unsuccessful. Attempts to contact the subject must be documented.
4. Voluntary withdrawal. The subject (or subject's legally acceptable representative) wishes to withdraw from the study. The reason for withdrawal, if provided, should be recorded in the

CRF. All attempts should be made to determine the underlying reason for the withdrawal and, where possible, the primary underlying reason should be recorded.

5. Study termination. The sponsor, IRB, or regulatory agency terminates the study.
6. Pregnancy. The subject is found to be pregnant.

Note: If the subject is found to be pregnant, the subject must be withdrawn immediately. The procedure is described in Section 8.1.10.

7. The investigator has determined that continued participation would pose an unacceptable risk to the subject.

Note: After the 30 minute wait period, subjects that develop local swelling at the site of the injection greater than 50mm diameter will have their next dose decreased by one step. Subjects having a Grade 1-2 systemic reaction will have their next injection decreased by two steps. Systemic reaction Grade 3 or more will require withdrawal from the study. Systemic reactions are defined by the World Allergy Organization anaphylaxis grading system (13).

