#### *7.1.4 Immunotherapy Dose and Regimen*

Recruited subjects alternate to be assigned either treatment set I or II (representing either placebo or active PMA treatment in a binded fashion). The assigned treatment set will remain for the duration of the study for each subject. On the day of an injection, 0.3ml from each of the appropriate vial set mix (A-C) will be combined in a sterile 5 ml bottle. Using a new sterile syringe, 0.15-0.60ml of the PMA solution or placebo will be removed for injection purposes according to the injection schedule (Appendix I). A sterile 27G ½ inch syringe will be used for administration. Immunotherapy will be administered bi-weekly in the study clinic for a total of eight consecutive weeks. Appendix I lists the precise immunotherapy injection schedule.

All patients are required to remain in the clinic under close observation by the study nurse for a period of 30 minutes following their injection. A physician is required to be present in the clinic at all times. In addition, one of the investigators must be present on campus and available by cell phone during scheduled treatment sessions. Emergency medications such as albuterol, oxygen, diphenhydramine, and at least two epi-pens will be readily available in the treatment area.

It is important to note that the maximum concentration of each individual allergen is quite low compared to more traditional immunotherapy regimens. The maximum PNU/ml (Protein Nitrogen Units) in vial #1 will be no more than about 180 PNU/ml per allergen (eg 0.9ml of 20,000 PNU/ml stock material into 100ml solution). In most cases the actual concentration of each stock allergen is much lower than 20,000 PNU/ml since the material may be provided as a mixture of several allergens. We would estimate therefore that subjects would receive no more than about 7.2 PNU of antigen contained in the highest injection (0.2ml Vial #2). Typically, allergens are administered via immunotherapy in a range of about 2000 PNU. Thus the dosage of each allergen is less than 0.36% of a typical dose administered in our clinics. The lower overall dosing scheme provided in this study would therefore be considered to be extremely safe with minimal adverse events.

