## **Appendix A Schedule of Study Procedures**

Study Week:	Screen (Week 1)	Washout (Week 1-2)	Treatment (Week 3-11)	Follow-up safety assessment (Week 14)
Visit Number:	1	N/A	2-17	18
Discussion and Recruitment	X			
Informed consent	X			
Inclusion/exclusion criteria	X			
Demographics and medical history	X			
Medication history	X			
Physical examination	X			
Vital signs	X		X	
Weight and height	X			
Concomitant medications	X	X	X	X
Concurrent medical conditions	X			X
Skin Testing	X			
Blood Draw	X			X
Post-immunotherapy safety f/u				X
Administer immunotherapy/safety f/u			X	
Clinical Survey (RQLQ) and TNSS	X		X	X
Site return compliance	X		X	X
PTE assessment	X	X		
AE assessment		X	X	X

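### The protocol sets the post-injection stay at 30 minutes in Sections 7.1.4 and 6.4 and at 60 minutes in Sections 8.3.3 and 1.2, and does not say which governs

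*Combined protocol and SAP*

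**What the plan says.** Two sections of the protocol give 30 minutes. Section 7.1.4 (Immunotherapy Dose and Regimen) makes it mandatory for all patients to "remain in the clinic under close observation by the study nurse for a period of 30 minutes following their injection". The note at the end of Section 6.4 opens its local-swelling rule with the same interval: "After the 30 minute wait period, subjects that develop local swelling at the site of the injection greater than 50mm diameter" have the next dose reduced by a step.

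Two sections give 60 minutes. Section 8.3.3 (Treatment Phase), describing the treatment visits, says: "A 60 minute post treatment in-clinic safety assessment will be conducted". Section 1.2 (Abstract and Study Design), describing the return visit for the first administration, says of the in-clinic safety evaluation: "The latter evaluation period will comprise approximately 60 minutes".

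The schedule in Appendix A lists only "Administer immunotherapy/safety f/u", with no duration. The Appendix J visit form has time fields beside the dose and beside the exit vitals, but no required interval between them. The SAP does not mention the observation period.

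**The concern.** A 60 minute in-clinic assessment cannot be completed for a subject who is free to leave at 30 minutes, so the two requirements cannot simply be run together as written. A nurse following Section 7.1.4 and a nurse following Section 8.3.3 would both be complying with the protocol while watching subjects for different lengths of time.

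Two things are at stake. The first is direct observation of immediate reactions, which is a matter of subject safety. The second is the local-swelling rule in Section 6.4. Its wording can mean swelling measured once 30 minutes have passed, or swelling that appears after that point. On the second reading, a subject released at 30 minutes has left before the swelling can be measured in clinic, while one held for 60 minutes may still be there. The same local reaction could then change the next dose for one subject and not for another.

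**Working it through.** The plan gives no figure to reproduce, and no sample size, power or event calculation enters. The check sets the statements side by side and then does simple arithmetic on observation time.

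| Place | Post-injection period | Scope as worded |
|---|---|---|
| Section 7.1.4 | 30 minutes | all patients, after injection |
| Section 6.4, note | 30 minutes | local-swelling rule |
| Section 8.3.3 | 60 minutes | visits 1 through 12 |
| Section 1.2 | about 60 minutes | return visit for administration |
| Appendix A | none given | visits 2 to 17 |
| Appendix J | none given; times recorded | each visit |

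**Could they be different procedures or visits?** The nouns differ (observation, wait, assessment, evaluation), but all describe the subject's time in clinic after an injection. Section 1.2, read alone, might concern the first dose only. Section 8.3.3 is not so limited: it applies 60 minutes to treatment visits generally, and those visits also fall under Section 7.1.4. The conflict therefore stands on Sections 7.1.4 and 8.3.3 alone.

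**How far does the 30 minutes reach in Section 6.4?** It introduces the local-swelling sentence only. The sentences on Grade 1-2 systemic reactions and on withdrawal for Grade 3 or more carry no time limit, so as written they apply whenever such a reaction occurs.

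**Size per subject.** The difference per injection is 60 − 30 = 30 minutes, or 0.5 h.

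- Appendix H lists injections at visits 2 to 17: 17 − 2 + 1 = 16. Required time is 16 × 30 = 480 min (8 h) under one rule and 16 × 60 = 960 min (16 h) under the other, a difference of 8 h.
- If Section 8.3.3 is held to visits 1 through 12 and Appendix H numbering is used, visits 2 to 12 give 11 injections: 11 × 0.5 = 5.5 h.
- If a first injection at visit 1 is counted, as Section 8.3.2 describes, there are 12: 12 × 0.5 = 6 h.

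**What does not depend on the figure?** Section 12.1.4 counts treatment-emergent events from the first dose to 30 days after the last. Section 9.2.1.2 has the investigator ask about adverse events at each visit and lets subjects report them at any other time. The SAP, under Secondary Outcomes, accepts events that are spontaneously reported or are elicited by questioning, examination or evaluation. None of these refers to the post-injection wait, and neither do the primary outcomes or Section 12.3.

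**The case against.** The strongest reply is that this is incomplete editing with little consequence. One 60 minute statement sits in an abstract and is approximate. The other is in a section whose visit count already disagrees with Appendices A and H. Appendix J records clock times, so the length of stay can largely be reconstructed. All of that is fair, but it neither removes the contradiction nor shows which figure was meant, and a form that records the time does not tell staff how long to wait.

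A reader might draw four stronger conclusions, which the documents do not support.

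- *That all the Section 6.4 reaction rules hang on the 30 minute reading.* Only the local-swelling sentence does. A systemic reaction at 45 minutes, for example, triggers the other rules under either period.
- *That reactions between 30 and 60 minutes drop out of the adverse event data.* They remain within the event definition and the collection routes after the subject leaves. What may be lost is direct observation and measurement, chiefly of mild, transient events.
- *That the comparison of adverse event rates between arms is biased.* This is a single-site, double-blind trial and nothing links either period to a treatment set, so any effect would be expected to fall on both arms alike.
- *That 288 hours of observation are in dispute across the trial.* That is 16 × 0.5 × 36, and it requires all 36 subjects to receive all 16 injections, although Section 12.3 sets 36 to allow for drop-out from a needed 28. On the narrower reading of Section 8.3.3 the same product is 11 × 0.5 × 36 = 198 or 12 × 0.5 × 36 = 216 hours. Clinic hours in any case do not measure missed reactions.

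Section 3.1 places the symptom peak in allergic rhinitis roughly an hour after allergen provocation. That concerns provocation rather than injection, and it does not decide between the two periods.

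**Conclusion.** This is a genuine internal inconsistency, two statements against two, with no rule of precedence. It bears on how long subjects are watched after each injection and on when the local-swelling rule is read, so it is more than clerical. Its size is a twofold difference, 30 minutes per injection. Per subject that is up to 8 hours if both periods are taken to cover all 16 Appendix H injections and the subject receives every one, or about 5.5 to 6 hours if Section 8.3.3 is held to its stated visits. That practice would actually vary between visits or subjects is a possibility left open by the text, not something the documents show. The efficacy conclusions do not turn on it.

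**What to change.** Reconcile Sections 1.2, 6.4, 7.1.4 and 8.3.3 to one stated post-injection observation period. If two distinct procedures are intended, say so, and give each its own duration and the visits it covers. Word the Section 6.4 local-swelling note so that it says when swelling is read relative to that period, and tie the Appendix J exit-vitals entry to the same point. Which period applies is for the sponsor and investigators to decide.

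The cost is a short protocol wording change and a small edit to the visit form. The consent pages are not part of the public document, so the sponsor should check whether they state an observation period that needs to match. No analysis, sample size or SAP text has to change.

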### 8.3.4 Final Visit or Early Termination

The Final Visit will be performed on visit 18 or at an Early Termination Visit. The following procedures will be performed and documented:

- Physical examination.
- Vital signs.
- Concomitant medications.
- Concurrent medical conditions.
- Efficacy assessment.
- Safety assessment.
- Blood draw.

For all subjects receiving study medication, the investigator must complete the End of Study CRF page.

### 8.3.5 Follow-up

Follow-up will begin the first day after the last injection and will continue until for 30 days at which time a final in-clinic visit (visit 18) will be conducted for a safety assessment and blood draw.

### 8.3.6 Post Study Care

The study immunotherapy will not be available upon completion of the subject's participation in the study. The subject should be returned to the care of a physician and standard therapies as required.

Subject to applicable laws and feasibility, access to the study immunotherapy may be available to individual subjects for whom the investigators deem the treatment to be essential and wherein the subject is at risk of significant morbidity or mortality. The investigator should contact the medical monitor to determine if access is possible.

## **9.0 PRETREATMENT EVENTS AND ADVERSE EVENTS**

### **9.1 Definitions**

#### **9.1.1 PTEs**

A PTE is defined as any untoward medical occurrence in a clinical investigation subject who has signed informed consent to participate in a study but prior to administration of any study medication; it does not necessarily have to have a causal relationship with study participation.

#### **9.1.2 AEs**

An AE is defined as any untoward medical occurrence in a clinical investigation subject administered a drug; it does not necessarily have to have a causal relationship with this treatment.

An AE can therefore be any unfavorable and unintended sign (eg, a clinically significant abnormal laboratory finding), symptom, or disease temporally associated with the use of a drug whether or not it is considered related to the drug.

#### **9.1.3 Additional Points to Consider for PTEs and AEs**

An untoward finding generally may:

- Indicate a new diagnosis or unexpected worsening of a pre-existing condition. (Intermittent events for pre existing conditions underlying disease should not be considered PTEs or AEs.)
- Necessitate therapeutic intervention.
- Require an invasive diagnostic procedure.
- Require discontinuation or a change in dose of study medication or a concomitant medication.
- Be considered unfavorable by the investigator for any reason.
- PTEs/AEs caused by a study procedure (eg, a bruise after blood draw) should be recorded as a PTE/AE.

Diagnoses vs signs and symptoms:

- Each event should be recorded to represent a single diagnosis. Accompanying signs or symptoms should NOT be recorded as additional AEs. If a diagnosis is unknown, sign(s) or symptom(s) should be recorded appropriately as a PTE(s) or as an AE(s).

Pre-existing conditions:

- Pre-existing conditions (present at the time of signing of informed consent) are considered concurrent medical conditions and should NOT be recorded as PTEs or AEs. Baseline evaluations (eg, laboratory tests, ECG, X-rays etc.) should NOT be recorded as PTEs unless

related to study procedures. However, if the subject experiences a worsening or complication of such a concurrent condition, the worsening or complication should be recorded appropriately as a PTE (worsening or complication occurs before start of study medication) or an AE (worsening or complication occurs after start of study medication). Investigators should ensure that the event term recorded captures the change in the condition (eg, “worsening of...”).

- If a subject has a pre-existing episodic condition (eg, gout, epilepsy) any occurrence of an episode should only be captured as a PTE/AE if the episodes become more frequent, serious or severe in nature, that is, investigators should ensure that the AE term recorded captures the change in the condition from Baseline (eg “worsening of...”).

Worsening of PTEs or AEs:

- If the subject experiences a worsening or complication of a PTE after starting administration of the study medication, the worsening or complication should be recorded appropriately as an AE. Investigators should ensure that the AE term recorded captures the change in the condition (eg, “worsening of...”).
- If the subject experiences a worsening or complication of an AE after any change in study medication, the worsening or complication should be recorded as a new AE. Investigators should ensure that the AE term recorded captures the change in the condition (eg, “worsening of...”).

Changes in severity of AEs /Serious PTEs:

- If the subject experiences changes in severity of an AE/serious PTE, the event should be captured once with the maximum severity recorded.

Preplanned surgeries or procedures:

- Preplanned procedures (surgeries or therapies) that were scheduled prior to signing of informed consent are not considered PTEs or AEs. However, if a preplanned procedure is performed early (eg, as an emergency) due to a worsening of the pre-existing condition, the worsening of the condition should be captured appropriately as a PTE or an AE. Complications resulting from any planned surgery should be reported as AEs.

Elective surgeries or procedures:

- Elective procedures performed where there is no change in the subject’s medical condition should not be recorded as PTEs or AEs, but should be documented in the subject’s source documents. Complications resulting from an elective surgery should be reported as AEs.

Insufficient clinical response (lack of efficacy):

- Insufficient clinical response, efficacy, or pharmacologic action, should NOT be recorded as an AE. The investigator must make the distinction between exacerbation of pre-existing illness and lack of therapeutic efficacy.

Overdose:

- Cases of overdose with the immunotherapy without manifested side effects are NOT considered PTEs or AEs, but instead will be documented on an Overdose page of the CRF. Any manifested side effects will be considered PTEs or AEs and will be recorded on the AE page of the CRF.

#### 9.1.4 SAEs

An SAE is defined as any untoward medical occurrence that at any dose:

1. Results in DEATH.
2. Is LIFE THREATENING.
  - The term “life threatening” refers to an event in which the subject was at risk of death at the time of the event; it does not refer to an event that hypothetically might have caused death if it were more severe.
3. Requires inpatient HOSPITALIZATION or prolongation of existing hospitalization.
4. Results in persistent or significant DISABILITY/INCAPACITY.
5. Leads to a CONGENITAL ANOMALY/BIRTH DEFECT.
6. Is an IMPORTANT MEDICAL EVENT that satisfies any of the following:
  - May require intervention to prevent items 1 through 5 above.
  - May expose the subject to danger, even though the event is not immediately life threatening or fatal or does not result in hospitalization.
  - Includes any event or synonym described in the Takeda Medically Significant AE List (Table 9.a).

**Table 9.a      Sponsor’s Medically Significant AE List**

Term	
Acute respiratory failure/acute respiratory distress syndrome	Hepatic necrosis
Torsade de pointes / ventricular fibrillation / ventricular tachycardia	Acute liver failure Anaphylactic shock

---

Malignant hypertension	Acute renal failure
Convulsive seizure	Pulmonary hypertension
Agranulocytosis	Pulmonary fibrosis
Aplastic anemia	Confirmed or suspected endotoxin shock
Toxic epidermal necrolysis/Stevens-Johnson syndrome	Confirmed or suspected transmission of infectious agent by a medicinal product
	Neuroleptic malignant syndrome / malignant hyperthermia
	Spontaneous abortion / stillbirth and fetal death

---

PTEs that fulfill 1 or more of the serious criteria above are also to be considered SAEs and should be reported and followed up in the same manner (see Sections 9.2.2 and 9.3).

It is important to note that out of more than 20,000 patients personally treated with the proprietary PMA allergen immunotherapy by [name] over the past 40 years, there HAS NEVER BEEN AN INCIDENT OF ANAPHYLAXIS OR SERIOUS SYSTEMIC REACTION attributed to the treatment. Epinephrine has never been required because of the treatment. Typical but uncommon side effects have included mild-moderate local swelling. These mild reactions occur at a rate of less than 20 percent.

